#### Responsiveness

ROC analysis and hypotheses testing (construct approach) using PRO change scores (i.e., change in PRO scores between two timepoints) will be used to evaluate responsiveness (i.e., see construct validity above). Responsiveness testing, as with all other aspects of SBQ-LC™ validation, will comply with COSMIN recommendations on methodological quality for studies of PRO validation.

### **10.3 Co-Production**

QSR NVivo12 will be used to manage, sort, code and organise the transcribed data. All transcribed data will be anonymised. Interview field notes, audio files and transcripts will be analysed using a rapid assessment procedure (RAP) sheet. The RAP sheet will be a working document summarising the main findings after each workshop.

## **11.0 Bio-samples**

### **11.1 Patient selection**

A sample of approximately 300 participants with Long COVID from each identified syndrome (symptom cluster) will be invited for bio-sampling (50 individuals per syndrome [total of four syndromes] plus 50 from each of the two control groups) 3 months following study enrolment.

### **11.2 Sample collection**

For venous blood draws, 1 x 10ml serum, 6 x 6ml Lithium Heparin and 8.5ml Paxgene DNA samples will be collected. SncRNAs will be extracted from a small sample of serum collected in a standard red-top tube (2ml aliquot). A maximum of 60 ml blood will be drawn from each participant.

The salivary sample collection will be performed by using a commercial buccal swab kit (DNA Genotek P-157 saliva collection kit). The buccal swab will be applied by the research team or the patient to the inside of the cheek near the floor of the mouth for a few seconds and causes no discomfort to the patient. Buccal swabs will not be collected from patients with bleeding or open sores in the mouth.

Once collected, blood and saliva samples will be labelled with the Global ID before being transported to the University of Birmingham Research Laboratory based at the Queen Elizabeth Hospital Birmingham. Research staff within the laboratory will be unable to identify research participants.

### 11.3 Sample processing

Processing will follow a standard laboratory research protocol. Processed samples will be stored and batch tested later. Samples may also be stored for repeat or further testing. Most samples will be analysed in Birmingham. However, serum/plasma analysed for proteins will be carried out using the Somalogic platform based in the USA. A material transfer agreement will be in place with other centres where testing will take place outside of UoB. Only pseudo anonymised samples will be transferred between sites and this will be recorded centrally so there is full traceability of samples.

The saliva kit includes a collection tube containing stabilisers that preserve the miRNAs at room temperature for up to eight weeks. RNA species will be extracted from the salivary swabs and serum using standard kits in accordance with the manufacturer's instructions. The sncRNA will then be analysed using Next Generation Sequencing analysis in the first instance. This produces a list of candidate biomarkers that includes all human sncRNAs (<200 basis). The candidate biomarkers that survive a set False Discovery Rate (typically 0.1) are taken forward for the next step, which includes amplification and measurement by standard qPCR. The results will be analysed and interpreted to detect unique biomarker profiles.

At the end of this study samples will be fully anonymised and stored for 5 years for use in other ethically approved research, either in the UK, or overseas or stored in a licensed tissue bank. There will be no mechanism to identify participants once samples have been anonymised.

Participants will be asked if they agree to consent that any leftover samples can be stored within the Clinical Immunology Service Laboratory/UoB Research Laboratories at the University of Birmingham for future ethically approved research. Only anonymised samples will be stored – the laboratory will hold no personal data.

All freezers used in this study will be temperature controlled and monitored 24 hours a day, with a fitted Tutela monitoring alarm system, in accordance with CIS protocols which have been United Kingdom Accreditation Service (UKAS) accredited.

### 11.4 Laboratory investigations

Participants will be screened with a comprehensive panel of autoantibodies related to systemic autoimmune conditions, a wide range of organ-specific autoantibodies, and a complete set of neuro-immunological markers for central and peripheral nervous system disorders. We will study any frequently recurring self-antigens to provide evidence of molecular mimicry between SARS CoV-2 antigens and the specific self-antigen. We will align these data with that from a separate study of hospitalised COVID-19 patients through our involvement in the UKRI funded Coronavirus Immunology Consortium (UK-CIC).

Participants will also have their serum analysed for proteins using the Somalogic platform. This will determine levels of 7000 proteins associated with pathogenesis of a range of long-term conditions and includes pro- and anti-inflammatory markers (IL1 $\beta$ , IL6, IL8, IL10, IL1ra, TNF $\alpha$ ) and markers of tissue damage and breakdown such as 3-methylhistidine for muscle catabolism. This will delineate mechanistic pathways for the different symptom clusters and will allow us to compare data with the PHOSPCOVID platform, which we contribute to in both the immunology and sarcopenia working groups. This work will complement our involvement in the UKRI-funded COVID-CNS consortium assessing mental health and cognitive decline in hospitalised COVID-19 survivors.

With consent, patient DNA/RNA will be studied/stored for genetic analysis.

These analyses will reveal the potential biological processes driving Long-COVID, some of which may be common to one or more syndromes and others that may be specific to one cluster. The identification of immune pathways associated with specific Long COVID syndromes will enable the identification of existing candidate drugs that target those pathways, for example B cell targeting therapies such as Rituximab if autoantibodies are raised in one or more clusters, or therapies such as Fisetin to remove senescent cells. This will ensure efficient targeting of therapies for acceleration of patient benefit.

Details of laboratory tests to be undertaken in this study are shown in Table 2.0.

**Table 2**

Sample Collected	Vacutainer Required	Total volume collected (mls)	Location	Downstream Application
Plasma	Green Lithium Heparin Vacutainer	6 x 6mls	IIA UoB Research Labs/Clinical Immunology Service Laboratory (CIS)	*Analysed for proteins using the Somalogic platform (USA)
Peripheral Blood Mononuclear Cells (PBMCs)	Green Lithium Heparin Vacutainer		IIA UoB Research Labs/Clinical Immunology Service Laboratory (CIS)	Immunophenotyping (flow cytometry), DNA/RNA isolation
Serum	Red Serum Vacutainer	1 x 10mls	IIA UoB Research Labs/Clinical Immunology Service Laboratory (CIS)	Analysed for autoantibodies (CIS)
Saliva	Commercial buccal swab kit (DNA Genotek P-157 Saliva collection kit)	Swab	IIA UoB Research Labs	SncRNA Analysis
RNA/DNA	PaxGene DNA tube	8.5ml	IIA UoB Research Labs/Clinical Immunology	Downstream genetic analysis

			Service Laboratory (CIS)	
Total volume:		Max 60mls whole blood		

*\*Samples to be batch sent to Somalogic for downstream analysis will be stored in temperature monitored -80 freezers prior to shipping.*

## 12.0 Study Withdrawals

### 12.1 Participant withdrawal

Participants will be made aware when they consent to the study that they will be free to withdraw at any time. Participants will be encouraged to complete the study measures, but they will not need to offer a reason for withdrawal. If participants are lost to follow-up their samples and data will be included. If a participant withdraws, they will be asked whether any of their collected samples to date can still be used. Alternatively, participants may opt to have their samples and data discarded. If data has already been analysed as part of a locked dataset then participants will be advised that it will not be possible to withdraw their data; however, samples will be destroyed.

### 12.2 Participant withdrawal - Co-production workshops

Due to the nature of data collection at the co-production workshops, it will not be possible to disaggregate individual participants' contributions from the discussions. Therefore, their data will be retained despite withdrawal. All data will be treated as confidential and anonymised both during analysis and in any subsequent reports.

As detailed in the PIS, for participants who later withdraw consent for photography, software will be used to remove the participant's image from the photograph.

## 13.0 Safety reporting

No risks are expected to arise from taking part in this observational study and no Serious Adverse Events are anticipated as a unique consequence of participation.

### 13.1 Expected Events

1. COVID-19 related Death
2. Flare-up of existing Long COVID symptoms and related hospitalisation.
3. Adverse Events are commonly encountered in patients having blood tests. However, blood testing is usually well tolerated. The most common adverse event is an individual feeling faint, during phlebotomy. Facilities, including a bed on which to lie, will be available to mitigate this if required. Sometimes there is bruising at the puncture site. This is a common adverse event and so will not be recorded or reported.

## 14.0 Sampling

### 14.1 Sample Size

To define Long COVID symptom clusters:

Reliable detection of clustered data via well-chosen combinations of these methods has been shown to require at minimum 20-30 observations per subgroup provided good cluster separation exists (effect size  $\Delta=4$  or over). We expect that with 500 patients in the long Covid cohort we will have power above 80% to detect well-separated clusters comprising at least 5% of the cohort for K=4 to K=6 clusters.

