#### **Establish a representative population-based cohort of individuals with Long COVID (Objective 1)**

A representative population-based cohort of non-hospitalised individuals with Long COVID will be established using primary care records in the Clinical Practice Research Datalink (CPRD) and recruitment through the Interventional Research Services Platform (IRSP). We will use linked data from the Second-Generation Surveillance PCR-confirmed COVID-19 registry to identify all confirmed COVID-19 patients in CPRD. Using linked Hospital Episode Statistics (HES) data we will identify and exclude hospitalised patients. Further details on each of the data sources is provided (Box 1).

All potential cases will be reported to the Clinical Practice Research Datalink's (CPRD) Interventional Research Services Platform (IRSP). This is a web-based research platform linked to CPRD's anonymised primary care database of coded clinical electronic health care data from approximately 1700 practices across the UK. The platform enables primary care staff to review pre-selected patient lists, confirm eligibility and invite patients to join a study. The selection criteria are applied within the CPRD IRSP, based on the predefined patient selection strategy. A delegated health professional at each practice can subsequently access the pseudonymised patient list, re-identify the patients, and review the clinical record to a set of screening questions. For patients that meet selection criteria, the primary care team will send out an invitation letter informing them about the study and containing key links and information required to enable enrolment onto the study.

Via IRSP, all potential cases will be presented to participating general practices to review their suitability for study recruitment. Those assessed as suitable for study recruitment will be sent an invitation letter to participate in the study. We aim to recruit a minimum of 2000 individuals with COVID-19. Individuals from underrepresented sociodemographic groups (e.g., Black and Minority Ethnic (BAME) and those from areas of high socioeconomic deprivation) will be oversampled. These individuals with COVID-19 (minimum n=2000) will be invited to report symptoms, quality of life and work capability through the Aparito Atom5™ digital platform. Data collected from this cohort of patients with COVID-19 will be used to identify a sub-cohort of patients with long-term symptoms of Long COVID (minimum n=500, aiming for n≥750).

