**Data-driven analysis to identify distinct Long COVID syndromes (Objective 4, part A)**

We will define distinct symptom clusters (syndromes) using linked data from CPRD and Atom5™ platforms. We will employ clustering algorithms that have been shown to work well in medical settings, with binary and mixed variables: (1) complete linkage hierarchical clustering; (2) probabilistic c-means cluster analysis; (3) density peaked clustering analysis. We will evaluate algorithm performance and the optimal number of clusters (e.g. by internal validation against a holdout dataset using metrics such as Gap statistic and silhouette index).

We will describe the epidemiology of patients within each Long COVID syndrome as well as health service use (primary care consultations, prescriptions, A&E attendances and hospital admissions) and mortality risk and compare these to both sets of matched control patients. We will identify whether Long COVID syndromes are

associated with particular population groups such as BAME groups, patients with long-term conditions, and other vulnerable population groups identified by Public Health England.

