### **Immunological phenotyping of Long COVID syndromes (Objective 5, part A)**

Long COVID is associated with both systemic and organ-specific sequelae, including changes in the central nervous system. These are reminiscent of autoimmune phenomena arising following infections. Often these are transient; however, in some individuals they persist and generate post-infectious autoimmune sequelae. To study this, we will invite patients to obtain bio samples (saliva and blood) for a minimum of 250 patients with Long COVID and 50 patients in each of the control groups. We will measure common autoantibody profiles and use both antibody and T cell screens to identify specific self-antigens associated with long COVID, which may allow the identification of potential immunotherapies.

The extended hyperinflammation and immune activation seen with COVID-19 is also likely to accelerate the ageing of the immune system, including the generation of pro-inflammatory, tissue damaging senescent T cells. We will assess this in a sample of each of the symptoms clusters in the Long COVID cohort, and both sets of matched control patients, to determine if there is a preponderance amongst one or more syndromes. Their presence will suggest the utility of interventions to reverse immune ageing such as use of rapamycin analogs.

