## **6.3 Matched controls - Group 2 (50 participants)**

### **6.3.1 Eligibility criteria**

Participants taking part in the study who have had a positive SARS CoV-2 RT-PCR test result in SGSS data linked to CPRD but not reporting symptoms on ATOM5™ beyond 12 weeks from the positive RT-PCR test result will comprise Control Group 1. These control participants will be propensity score-matched to participating Long COVID patients.

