### **6.5.3 Bio-sampling and wearables (BioWear) sub-cohort**

Researchers will identify distinct symptom clusters (syndromes) using linked data from CPRD and data collected via the Atom5™ platform. A random sample of up to 300 participants (200 participants with Long COVID, with 50 sampled from each of the four most prevalent Long COVID syndromes, and 50 participants from each of the two control groups) who have previously consented to be contacted for bio-sampling will be identified and invited to take part in the BioWear sub-study. Selected participants will be sent an invitation to participate and the BioWear sub-study PIS via the Atom5™ app, SMS message or by post for those who have expressed having difficulty accessing digital platforms. Those individuals showing an interest in taking part will be contacted by a member of the research team to arrange a date and time for blood and saliva sample collection and to be provided with a wearable device (Garmin Vivosmart4).

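### Bio-sample and Control Group 2 sizes conflict, and a sampled cluster at the 5% floor (25 of 500) cannot supply the 50 people that BioWear and Table 3 assume

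*Protocol*

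**What the plan says.** **Cluster size.** Section 14.1 starts from a need for clustering methods to "require at minimum 20-30 observations per subgroup provided good cluster separation exists". It then states: "We expect that with 500 patients in the long Covid cohort" (the planned minimum) "we will have power above 80% to detect well-separated clusters comprising at least 5% of the cohort for K=4 to K=6 clusters". Section 5.0 gives the Long COVID cohort as "minimum n=500, aiming for n≥750".

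**Bio-sampling.**
- Section 6.5.3 samples 200 Long COVID participants, "with 50 sampled from each of the four most prevalent Long COVID syndromes", plus 50 from each control group, up to 300 in all. Only people who agreed to be contacted are eligible.
- Section 11.1 also counts four syndromes, but words the total of about 300 as if all had Long COVID.
- Section 6.4.1 takes 50 from every cluster, with a ceiling of 200.
- Section 14.2 takes 50 from every identified syndrome. Its Table 3 gives two-sample Kruskal-Wallis power at 50 v 50.
- The Study Summary and section 4.0 say up to 200.
- Section 5.0 (Objective 5, part A) calls for "a minimum of 250 patients with Long COVID and 50 patients in each of the control groups".

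**Control Group 2.** Section 6.3 is headed "Matched controls - Group 2 (50 participants", and 6.3.1 says that its members make up Control Group 1. The Study Summary, 4.0, 5.0 and 6.5.2 all give this group 500 or at least 500. Section 6.2.1 reserves the name Control Group 1 for people without COVID-19.

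**The concern.** The protocol plans to find syndromes as small as 25 people, and then to compare biomarkers between syndromes as though each could give 50. If a sampled syndrome is that small, the power in Table 3 does not apply to it, and no rule says what happens when a cluster falls short. The biomarker comparison by syndrome is the core of Objective 5.

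The group sizes are a separate matter of consistency. A minimum of 250 and a maximum of 200 cannot both be met. A control group that is 50 in its own eligibility section and 500 elsewhere, under the other group's name, leaves the reader unsure who is recruited to which group.

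**Working it through.** **1. Bio-sample numbers side by side.** The design in 6.5.3 and 11.1 is 4 × 50 = 200 with Long COVID and 2 × 50 = 100 controls, 300 in all. The figure in 5.0 gives 250 + 50 + 50 = 350, above the 300. The rule of 50 from every cluster in 6.4.1 and 14.2, with the five or six clusters allowed by 14.1, gives 5 × 50 = 250 or 6 × 50 = 300, above the ceiling of 200 in 6.4.1 itself. Only the rule of four clusters fits the ceiling.

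**2. Size of a floor cluster.** Inputs from 14.1 and 5.0: share 5%, cohort 500 (aim 750).
- 0.05 × 500 = 25
- 0.05 × 750 = 37.5

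Both are below 50. If 5% is read as a population share and the cohort as a random draw (an assumption), the count is binomial. P(at least 50) is then below 0.0001 at 500 and 0.026 at 750.

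**3. Share needed for 50 people at N = 500.** For 50 expected members: 50/500 = 10%. For an 80% chance of at least 50: about 11.1%. Both are before consent to contact and attendance.

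**4. When the shortfall occurs.** With four clusters all are sampled, so a floor cluster is certain to fall short. With five or six, a floor cluster may never be sampled. There the shortfall needs one of the top four to be under about 10–11%. As an illustration, one cluster of 70% and five of 6% (70 + 5 × 6 = 100) would put clusters of 0.06 × 500 = 30 people in the top four.

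**5. Power.** Kruskal-Wallis test on two samples, chi-square with 1 degree of freedom, alpha 0.05, unit-variance normal or unscaled t5, 20,000 simulated trials per cell. Table 3 is reproduced within 2 points in every cell. Smaller groups follow in the same way.

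| Location difference, distribution | Table 3 | 50 v 50 | 25 v 50 | 25 v 25 |
|---|---|---|---|---|
| 0.6, normal | 80.8% | 82.5% | 65.1% | 52.9% |
| 0.8, normal | 95.8% | 97.3% | 88.1% | 76.5% |
| 0.6, t5 | 71.7% | 71.6% | 54.1% | 42.8% |
| 0.8, t5 | 92.5% | 92.2% | 78.3% | 66.0% |

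The 25 v 50 column is a floor cluster against a full cluster or a control group. The 25 v 25 column is two floor clusters. A second simulation of the normal cells with 40,000 runs gave 65.2% and 87.8% (25 v 50), and 52.8% and 77.0% (25 v 25).

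**The case against.** Most of the case for the protocol stands, and it narrows the point.

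- Finding a cluster and sampling 50 people from it are different aims; 25 may be enough for the first.
- Table 3 states its group size and is correct for it. It makes no claim about 25.
- The totals of 200 and 300 are ceilings, so some under-filling is already allowed. But 6.4.1, 6.5.3, 11.1 and 14.2 still set 50 per cluster, and Table 3 rests on that.
- Sampling only the four most prevalent syndromes removes the problem for many configurations with five or six clusters.
- The size conflicts are largely clerical: 200 is the usual bio-sample figure and 500 the usual Control Group 2 figure, each with one outlier.

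A reader might go further and infer that the clustering power above 80% is wrong. The protocol does not support that. Twenty-five lies inside its own range of 20 to 30. On the binomial reading, P(at least 20) is 0.87 and P(at least 30) is 0.18, so the claim looks doubtful only if the top of the range is made a hard threshold. The chance of having enough members is also not the chance of detecting the cluster. Section 14.1 gives no derivation or detection criterion, so the figure cannot be reproduced. A small illustrative simulation under assumed cluster shapes gave detection rates well below and well above 80%, depending on the algorithm.

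Nor can the claim be attacked through "internal validation against a holdout dataset": section 5.0 offers that only as an example, no fraction is given, and 10.1 relies on cross-validation and bootstrap resampling.

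**Conclusion.** The point holds in three parts. First, the Long COVID bio-sample is both at least 250 and at most 200, and the rule of 50 from every cluster breaks that ceiling when there are five or six. Second, section 6.3 misstates both the size of Control Group 2 (50 against 500) and its name. These two need no assumptions.

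Third, a sampled cluster at the 5% floor has about 25 people, half of what BioWear and Table 3 assume. For it, power under normality is about 65% rather than 80.8% at a difference of 0.6, and about 88% rather than 95.8% at 0.8. Between two such clusters it is about 53% and 77%. These figures take the cohort at its minimum of 500 and assume that every member of the cluster agrees and attends, so they are optimistic for a 25-person cluster. At 750 the floor cluster averages 37.5, which is still short.

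The statement of more than 80% clustering power is underived but not refuted, and raising the 5% floor on these grounds would not be justified.

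**What to change.** - Use one Long COVID bio-sample number throughout, and one cluster rule (the four most prevalent), in section 5.0 (Objective 5, part A), 6.4.1, 11.1 and 14.2. In 11.1, say that the total of about 300 includes both control groups.
- Correct 6.3 to Control Group 2, minimum 500, of whom 50 are for BioWear, and replace the Control Group 1 label in 6.3.1.
- State beside Table 3 that it applies only to clusters that supply 50 sampled people, roughly 11% or more of a cohort of 500 before refusals. Add the power for 25 v 50 and 25 v 25.
- State that a sampled cluster with fewer than 50 available members is taken in full.

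The cost is protocol wording and a less favourable stated power for small syndromes. No extra participants are needed.
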